9. STUDY PERIODS

9.1. Screening and Eligibility

Subjects must sign the informed consent before any study-specific procedure can be performed (Section 10.1). The Screening Period will last up to 4 weeks. A summary of Screening and enrollment events is provided in the Schedules of Assessments ([Appendix 1](#) and [Appendix 2](#)).

Inclusion and exclusion criteria are listed in Section 4.1 and Section 4.2, respectively. Subjects who have met all inclusion/exclusion criteria requirements may be randomized into the study.

Screening procedures must be completed within 28 days prior to Day 1. The Medical Monitor should be consulted to see whether repeated testing is needed if the subject is planned to be randomized > 28 days from the signing of the informed consent form (ICF). Rescreening procedures are described in Section 10.2.1.

Subjects with a Screening Visit 12-lead ECG showing a second- or third-degree AV block, sick sinus syndrome without a functional pacemaker, periods of asystole > 3 seconds without an implanted cardiac pacemaker, PR interval \geq 200 ms, or QTcF \geq 450 ms (men) or QTcF \geq 470 ms (women) are not eligible for rescreening.

Eligibility for the Open-Label Extension Period will be assessed at the Week 24 visit and is defined in Section 4.3.

9.2. Randomization and Double-Blind Treatment Period

Subjects enrolled with this version of the protocol (Amendments 2.0 and 2.1) who complete all Screening requirements and remain eligible for the study will be randomized in a 4:1:2 ratio to receive etrasimod 3 mg, etrasimod 2 mg, or placebo orally once daily for 24 weeks in the Double-Blind Treatment Period. Subjects will self-administer study drug, except on study visit days, as described in Section 6.3. Study visits and assessments will be conducted according to the Schedule of Assessments (Appendix 2).

9.2.1. Day 1 Pre-Randomization

At the Day 1 visit, prior to randomization, inclusion and exclusion criteria must be evaluated again. To this end, vital signs including HR and BP must be measured first, followed by 12-lead ECG. Vital signs may be repeated up to 3 times to confirm abnormal readings.

Subjects with the following must not be randomized and should be considered screen failures:

- Sitting vital sign assessment: HR < 50 bpm, systolic BP < 90 mm Hg, OR diastolic BP < 55 mm Hg
- 12-lead ECG showing a second- or third-degree AV block, periods of asystole > 3 seconds, PR interval \geq 200 ms, or QTcF \geq 450 ms (males) or QTcF \geq 470 ms (females)

All predose 12-lead ECGs should be obtained prior to blood sample collection.

Women of childbearing potential will have a urine pregnancy test prior to randomization (Section 10.2.6).

Subjects who continue to meet all inclusion criteria and no exclusion criteria will be randomized as outlined in Section 6.4.

Once eligibility is confirmed, a Holter monitor will be placed on the subject and continuous Holter recording should begin approximately 15 minutes before first administration of study drug and continue for 8 hours post-treatment administration as described in Section 10.5.7.5.

9.2.2. Day 1 Post-Randomization

Randomization may occur on Day 1 after all eligibility criteria have been confirmed. It is recommended that procedures are performed in a consistent order and at approximately the same time of day for each visit. The recommended sequence of events is as follows:

- Questionnaire administration
- AE review
- Vital signs (performed with subject in the seated position)
- 12-lead ECG (performed with subject in the supine position)
- Physical examination including disease severity assessments
- Blood sample collection for laboratory tests and predose PK sampling
- Urine sample for urinalysis, drug screen, and pregnancy test if applicable

Day 1 pre-randomization vital signs (resting HR, BP, body temperature, and respiratory rate) will be used as Baseline measurements. The lowest predose HR measurement will be used for comparison to the postdose HR measurement. Refer to Section 10.5.7.5 for detailed guidance on Holter monitoring and Section 10.5.7.4 for detailed guidance on cardiac monitoring following administration of the first dose and subject discharge criteria postdose.

After dosing on Day 1:

- At Hours 1, 2, and 3 (± 15 minutes) postdose, HR and BP will be assessed with the subject in the seated position, with the time recorded. If the subject has an HR < 50 bpm, or if cardiovascular symptoms develop (eg, chest pain, dizziness, palpitations, and/or syncope associated with reduction of HR), the subject should remain closely monitored, including 12-lead ECGs as clinically indicated, until the discharge assessment at 4 hours.
- At the Hour 4 (± 15 minutes) discharge assessment, HR and BP will be assessed with the subject in the seated position; a 12-lead ECG will also be performed in the supine position. Subjects may be discharged from the clinic after the 4-hour assessment if they meet the criteria described in Table 7. Subjects not meeting the discharge criteria will require extended monitoring (Section 10.5.7.4).
- Subjects experiencing a clinically relevant treatment-related symptomatic event (eg, chest pain, dizziness, palpitations, and/or syncope) associated with reduction of HR together with clinically relevant 12-lead ECG changes at any time during the 4-hour monitoring period should be discontinued from study drug (Table 8).

To minimize the risk of unintentional unblinding of treatment assignment, refer to guidance regarding disclosure of HR data discussed in Section 6.6.

A blood sample for PK assessment is to be taken 4 hours (± 15 minutes) postdose after the ECG on Day 1.

9.2.3. Double-Blind Treatment Period Study Visits After Day 1

There is no in-clinic cardiac monitoring at Week 1. However, all subjects will undergo Holter monitoring as described in Section 10.5.7.5 at the Week 1 visit.

After the Day 1/Baseline study visit, a visit window of ± 1 day is permitted for the Week 1 (Cohort 2 only) and a visit window of ± 3 days is permitted for the other study visits during the 24-Week Double-Blind Treatment Period.

Negative pregnancy test results must be documented for all women of childbearing potential prior to dosing at each study visit where study drug is administered. At each study visit, blood sample collections should be performed prior to dosing unless specified otherwise (eg, postdose PK assessments).

Subjects who discontinue treatment prematurely should have an ET visit within 1 week of when the last dose of study drug was taken (Section 9.5).

9.3. Open-Label Extension Period

After completing the 24-week Double-Blind Treatment Period, eligibility for participation in the Open-Label Extension Period will be determined (Section 4.3). All eligible subjects in Cohort 1 will receive etrasimod 2 mg orally, for at least 1 week during the Open-Label Extension Period. Subjects in Cohort 1 will transition to 3 mg at the Week 25 visit or at their next Open-Label Extension study visit after the implementation of Amendments 2.0 and 2.1. Subjects in Cohort 2 will receive etrasimod 2 mg orally, once daily for 1 week during the Open-Label Extension Period and then transition to etrasimod 3 mg orally, once daily for the remainder of the Open-Label Extension Period. Subjects from Cohort 1 who are already in the Open-Label Extension Period at the time of Amendments 2.0 and 2.1 implementation may be allowed to continue on etrasimod 2 mg at the Investigator's discretion provided that they have achieved a SALT I score ≤ 20 . A visit window of ± 3 days is permitted for all study visits during the 28-week Open-Label Extension Period, except for Week 25, for which a visit window of ± 1 day is permitted.

For subjects that continue into the Open-Label Extension Period cardiac monitoring will be performed for at least 4 hours after dosing, as outlined in Section 10.5.7.4.

The recommended sequence of events presented for Double-Blind Treatment Period Day 1 (Section 9.2.2) should be followed for visits during the Open-Label Extension Period, where applicable, with study drug being administered after blood sample collection.

Subjects will undergo Holter monitoring as described in Section 10.5.7.5 after dosing at the Week 24 visit, and at the Week 25 visit or following transition from 2 mg to 3 mg in the Open-Label Extension Period.

If a subject ends study drug prior to Week 52, the ET visit assessments (ie, Week 52 assessments; Section 9.5) should be performed within 1 week of the last dose of study drug.

9.4. Follow-Up/End of Study

Subjects who complete the Open-Label Extension Period will return for Safety Follow-Up Visits 2 weeks (± 3 days) and 4 weeks (± 3 days) after the last dose of study drug (which corresponds

to Week 54 and Week 56, respectively). Visit assessments are detailed in the Schedules of Assessments ([Appendix 1](#) and [Appendix 2](#)).

Subjects who terminate the study drug early in the Double-Blind Treatment Period or Open-Label Extension Period should have Safety Follow-Up Visits 2 weeks (± 3 days) and 4 weeks (± 3 days) after the last dose of study drug.

The final Safety Follow-Up Visit (ie, SFU 2) will also be the End of Study Visit.

All AEs should be recorded for up to 30 days after last dose of study drug (Section [10.5.8.2.2](#)).

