3.4. End of Study

A subject is considered to have completed the study if he/she has completed all phases of the study, including the last study visit (ie, Safety Follow-Up [SFU] 2).

The end of the study is defined as the date of the last study visit of the last subject in the study globally.

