8. REMOVAL OF SUBJECTS FROM THERAPY OR ASSESSMENT

8.1. Discontinuation of Study Drug

Study drug *must* be discontinued in the following instances:

- Unacceptable AE or AE that, in the judgment of the Investigator, is considered to not be in the best interest of the subject to continue study drug
- Subject request to discontinue for any reason
- Pregnancy during the study (Section [10.5.9](#))
- Termination of the study by the Sponsor or at the request of a regulatory agency or an Institutional Review Board (IRB) or Independent Ethics Committee (IEC)
- Lost to follow-up
- Criteria met from cardiac HR monitoring to discontinue study drug (Section [10.5.7.4](#))
- Confirmed lymphocyte measurement $< 0.2 \times 10^9$ cells/L (Section [10.5.7.2](#))
- Received a prohibited concomitant medication that required discontinuation of study drug (Section [6.8.2](#))

- Other

Study drug *may* be discontinued in the following instances:

- Subject noncompliance
- Protocol deviation
- Drug-induced liver injury (Section 10.5.7.1)

Subjects who discontinue treatment prematurely, regardless of the reason, should be instructed to return for an ET visit within 1 week of when the last dose of study drug was taken, and for Safety Follow-Up Visits 2 weeks and 4 weeks after the last dose of study drug (ie, SFU 1 and SFU 2) (Appendix 1 and Appendix 2). If a subject fails to attend the follow-up visits, all reasonable efforts will be made to contact the subject to ensure that he/she is in satisfactory health. All contacts and contact attempts must be documented in the subject's medical record.

Whenever possible, subjects should continue on study and complete the remaining study visits and assessments even when study drug has been discontinued.

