9.5. Early Study Drug Termination

Subjects who stop taking study drug before Week 52 will return to the clinic for an ET visit. ET visit assessments are detailed in the Schedules of Assessments ([Appendix 1](#) and [Appendix 2](#)). The ET visit should occur within 1 week of the last dose of study drug. Site staff will work with subjects who withdraw early to obtain as much follow-up data as possible. Lymphocyte counts should be monitored until returned to approximately Baseline or stable. Whenever possible, subjects should continue in the study even if study drug has been discontinued. Subjects who discontinue study drug, but who consent to remain in the study will continue to comply with study visits and assessments.

Subjects who terminate the study drug early in the Double-Blind Treatment Period or Open-Label Extension Period should have Safety Follow-Up Visits 2 weeks and 4 weeks (± 3 days) after the last dose of study drug as described in Section [9.4](#).

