11.2. Determination of Sample Size

Subjects will be randomized as follows:

- Cohort 1: 36 subjects in 2:1 randomization ratio (24 subjects to etrasimod 2 mg and 12 subjects to placebo)
- Cohort 2: 42 subjects with SALT I < 95 at Baseline in 4:1:2 randomization ratio (24 subjects to etrasimod 3 mg, 6 subjects to etrasimod 2 mg, and 12 subjects to placebo)

Assuming a 15% drop-out rate from the study over 24 weeks, at least 35 treatment completers (20 subjects to etrasimod 3 mg, 5 subjects to etrasimod 2 mg, and 10 subjects to placebo from Cohort 2; plus subjects from Cohort 1 with SALT I < 95 at Baseline) at Week 24 will provide at least 80% and 47% power to detect a treatment difference of 20% for etrasimod 3 mg and etrasimod 2 mg from placebo, respectively, in the percent change from Baseline in SALT I at Week 24 by a 2-sample t-test using a 2-sided significance test level of 0.05 and common standard deviation (SD) of 17.8%.

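### Protocol 9.4 makes SFU 2 the End of Study Visit with no exception for subjects who stop drug before Week 24, although 8.1 and 9.5 ask those subjects to stay on study

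*Protocol*

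**What the plan says.** **Text that points to closing the subject at SFU 2.** Protocol 9.4 gives subjects who stop drug early, in either treatment period, safety follow-up visits 2 and 4 weeks (± 3 days) after the last dose. The next sentence reads "The final Safety Follow-Up Visit (ie, SFU 2) will also be the End of Study Visit". Protocol 3.4 says "A subject is considered to have completed the study if he/she has completed all phases of the study, including the last study visit" and identifies that visit as SFU 2. SAP 3.4 mentions only the two SFU visits for early stoppers.

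**Text that points to retention.** Protocol 8.1: "Whenever possible, subjects should continue on study and complete the remaining study visits and assessments even when study drug has been discontinued". Protocol 9.5: "Whenever possible, subjects should continue in the study even if study drug has been discontinued". Section 9.5 adds that those who consent to remain keep to the study visits and assessments. The footnote to the Week 52/ET column in Appendices 1 and 2 repeats the instruction to stay in the study.

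**Text in between.** Protocol 9.6 defines the End of Study Visit as the date of the final study contact and gives SFU 2 as an example of such a contact.

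**Analysis side.** SAP 4.3 analyses a visit as scheduled when it is available. ET and unscheduled measurements are used only if they fall in the Table 1 windows. For subjects never treated in the open-label extension (OLE), the Week 24 window runs from Day 155 to last treatment day + 6. Contacts from last treatment day + 22 to the last contact belong to SFU 2.

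**The concern.** For an early stopper, SFU 2 is tied to the last dose, while Week 24 is tied to randomisation. If SFU 2 ends the subject's participation, the Week 24 SALT I score is not collected even though the subject may be willing to give it. That score is the primary endpoint and the basis of all secondary endpoints.

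Under SAP 5.3 a missing score is not imputed in the MMRM, which relies on missingness at random, and it counts as non-response in the CMH analyses. The SAP 10.1 sensitivity analyses are multiple imputation conditional on treatment, disease duration and SALT I history, or observed-case models in other sets or with other covariates. None of them examines dropout that depends on the unseen outcome. If subjects stop because hair does not regrow, or because of drug effects, collecting the value is therefore the main protection. Two sites reading different sections could also treat the same kind of subject differently.

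**Working it through.** **1. The plan's own figures.** Protocol 11.2 assumes: "Assuming a 15% drop-out rate from the study over 24 weeks, at least 35 treatment completers", made up of "20 subjects to etrasimod 3 mg, 5 subjects to etrasimod 2 mg, and 10 subjects to placebo from Cohort 2". It states that these "will provide at least 80% and 47% power to detect a treatment difference of 20" points, "by a 2-sample t-test using a 2-sided significance test level of 0.05 and common standard deviation (SD) of 17.8" (percent).

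Noncentrality = difference / (SD × √(1/n1 + 1/n2)), with df = n1 + n2 − 2:
- 3 mg, 20 v 10: 20 / (17.8 × √0.15) = 2.90, df 28, power 0.7997 (stated 80%).
- 2 mg, 5 v 10: 20 / (17.8 × √0.30) = 2.05, df 13, power 0.4759 (stated 47%).
- Drop-out: 24, 6 and 12 × 0.85 = 20.4, 5.1 and 10.2, and 35 / 0.85 is about 41.2, which rounds up to 42.

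The figures reproduce, and they already allow for losing 15% by Week 24.

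**2. When SFU 2 comes before Week 24.** Let t be the last-dose day (Days 1 to 168). SFU 2 is at t + 28. The Week 24 visit is at Day 169, with Day 166 the earliest in-window day.
- Before the nominal visit: t + 28 < 169, so t ≤ 140.
- Before the earliest in-window visit: t + 28 < 166, so t ≤ 137.
- With the ± 3-day windows the limit runs from t ≤ 134 (t + 31 < 166) to t ≤ 143 (t + 25 < 169).

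Example: last dose on Day 57 (Week 8). SFU 2 is at 57 + 28 = Day 85, and 169 − 85 = 84 days (12 weeks) then remain to Week 24.

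**3. Share of early stoppers exposed if 9.4 is read literally.** The documents give no stop-time distribution, so every row is an assumption, using t ≤ 137.

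| Assumed stop times | Share with SFU 2 before Day 166 |
|---|---|
| Linearly front-loaded | 97% |
| Uniform | 137/168 = 82% |
| Linearly back-loaded | 67% |
| All in the last 8 weeks (uniform) | 25/56 = 45% |
| All in the last 4 weeks | 0% |

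**4. Whether the ET visit rescues the endpoint.** The Week 24 window for a subject never treated in the OLE contains a day only if t + 6 ≥ 155, so t ≥ 149. That is 20 of 168 possible stop days (12%).

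**5. What the SAP does with an off-drug Week 24 score.** Take the Day 57 stopper seen on Day 169. The Week 24 window would run from Day 155 to Day 57 + 6 = 63, which is empty. SFU 2, listed in the table's OLE block, runs from Day 57 + 22 = 79 to last contact and so contains Day 169. The score counts as Week 24 only if it is entered as the scheduled visit. If it is recorded as unscheduled, it is not used for Week 24.

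**6. Ceiling on what retention could add.** If every Cohort 2 subject had a Week 24 value:
- 24 v 12: 20 / (17.8 × √0.125) = 3.18, df 34, power 87.0%.
- 6 v 12: 20 / (17.8 × √0.25) = 2.25, df 16, power 56.0%.

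This is optimistic. It assumes that all drop-out is recoverable and that off-drug values keep the same effect and SD.

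**The case against.** The strongest reply is that the protocol can be read as consistent. Section 9.6 defines End of Study as the final contact, so for a retained subject it is a later visit than SFU 2. Sections 8.1 and 9.5 each give the SFU visits and the request to continue side by side, and two extra safety visits fit within a roughly four-weekly schedule. Section 3.4 defines completion and does not tell a site to close anyone out. The retention instruction appears four times, and no text cancels the remaining visits.

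Much of this stands. A reader might infer that a site cannot satisfy both rules, or that most early stoppers will lose their Week 24 score. The documents do not support either: both sets of visits can be done, and under 8.1, 9.5 and 9.6 the loss for subjects who consent to stay is zero.

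A reader might also multiply the 15% drop-out by about 83% (140/168) and count 42 × 0.15 × 0.83 ≈ 5 or 78 × 0.15 × 0.83 ≈ 10 subjects lost. That does not follow. The 15% is drop-out from the study, including withdrawals and losses that no wording recovers. It is not a rate of stopping drug. The 83% assumes uniform stop days. And 78 is not the primary-analysis denominator, because the FAS excludes Baseline SALT I of 95 or more, which Cohort 1 entry (50 or more, Protocol 10.3.1) could include. Nor does the wording pull power below the stated figures.

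What remains is that 9.4 speaks without exception directly after addressing early stoppers. Section 9.5 refers the reader to 9.4 for the SFU visits, and 9.4 does not repeat the retention rule. The definition in 9.6 does not settle the matter, because which contact is final depends on which section the site follows.

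**Conclusion.** The point holds as a conflict of wording that puts primary endpoint data at risk. It does not show that data will be lost. Read literally, 9.4 with 3.4 lets a site close a consenting early stopper before Week 24 when the last dose is on or before about Day 137 to 140. The share of early stoppers exposed ranges from 0% to 97% across the assumed stop-time patterns, and the number of subjects cannot be estimated from the documents. The stated power stands. The stakes are avoidable missing data, possible bias if stopping is related to outcome, and uneven site practice. SAP Table 1 adds a second route to the same loss, even for subjects who are retained.

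**What to change.** - **Protocol 9.4 and 3.4**, reconciled with 8.1, 9.5 and 9.6: for subjects who stop study drug in the double-blind period and consent to remain, state that SFU 1 and SFU 2 are safety visits additional to the remaining scheduled visits, and that the End of Study Visit is the final study contact, no earlier than Week 24. Week 24 is a floor and should not narrow the 8.1 request for all remaining visits.
- **Appendices 1 and 2**: state which Week 24 efficacy assessments apply off drug, at least SALT I.
- **SAP Table 1**: for subjects who stopped drug but stayed on study, let the Week 24 window extend past last treatment day + 6 and take precedence over the SFU 2 window, so that an off-drug Week 24 SALT I is analysed as Week 24 however the visit was labelled.

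The cost is a short protocol clarification, one SAP edit and a few off-drug visits that 8.1 and 9.5 already request. No dosing or stopping rule changes.

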9.5. Early Study Drug Termination

Subjects who stop taking study drug before Week 52 will return to the clinic for an ET visit. ET visit assessments are detailed in the Schedules of Assessments ([Appendix 1](#) and [Appendix 2](#)). The ET visit should occur within 1 week of the last dose of study drug. Site staff will work with subjects who withdraw early to obtain as much follow-up data as possible. Lymphocyte counts should be monitored until returned to approximately Baseline or stable. Whenever possible, subjects should continue in the study even if study drug has been discontinued. Subjects who discontinue study drug, but who consent to remain in the study will continue to comply with study visits and assessments.

Subjects who terminate the study drug early in the Double-Blind Treatment Period or Open-Label Extension Period should have Safety Follow-Up Visits 2 weeks and 4 weeks (± 3 days) after the last dose of study drug as described in Section [9.4](#).

9.6. End of Study Visit

The End of Study Visit for an individual subject is defined as the date of the final study contact (eg, the final Safety Follow-Up Visit [ie, SFU 2]) when assessments or procedures are done.

10. STUDY ASSESSMENTS AND PROCEDURES

10.1. Subject Informed Consent

The Investigator, or a person designated by the Investigator, will obtain written informed consent from each subject before any study-specific activities are performed (Section [12.3](#)).

10.2. Screening and Eligibility

Subject eligibility will be assessed based on protocol inclusion and exclusion criteria as outlined in Section [4.1](#) and Section [4.2](#). All Screening evaluations must be completed and reviewed to confirm potential subjects meet all eligibility criteria.

Screening procedures must be completed within 28 days prior to receiving the first dose of study drug ([Appendix 1](#) and [Appendix 2](#)).

An additional eligibility assessment will be performed at Week 24 to determine eligibility to continue into the Open-Label Extension Period, as outlined in Section [4.3](#).

